4.4.3 Secondary Efficacy

Secondary efficacy will be measured by the proportion of subjects achieving hemostasis of the treated bleeding site at 5 minutes. The hemostasis status at 5 minutes will be used to define this endpoint. The proportion of subjects achieving hemostasis will be summarized by treatment group. The difference between groups will be reported, along with the 95% confidence interval of the difference. Non-inferiority will be evaluated by comparing the upper bound of the confidence interval for the difference in treatment proportions ($P_{Control} - P_{PerClot}$) to the non-inferiority margin of 0.10. If the upper bound is found to be less than 0.1, the null hypothesis will be rejected and treatment will be considered non-inferior to control.

This analysis will be performed on the AT, ITT, and PP populations. The AT population will serve as the primary analysis population for the evaluation of the secondary efficacy endpoint. Analyses based on the ITT and PP populations will be presented as supportive analyses. Additionally, the number of subjects in whom hemostasis is achieved at 5 minutes, but has a re-bleed after the 5 minute assessment will be summarized. A sensitivity analysis of the endpoint will be conducted where all subjects that achieved hemostasis at 5 minutes, but did not maintain it after the assessment will be counted as ‘failures’ in the analysis. The use of Clinical Evaluation Committee adjudications for this endpoint will be the same as for the primary efficacy endpoint, to provide a supplementary secondary analysis of this secondary endpoint.

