4.2.1.1 Sample Size Justification

The sample size was calculated based on the following assumptions:

- One-sided alpha = 0.025;
- Minimum 80% power;
- Non-inferiority margin $\delta = 0.10$;
- Expected 7 minute hemostatic success rate in the PerClot group is 90%; and
- Expected 7 minute hemostatic success rate in the control group is 90%.
- Randomization allocation of 1:1

A sample size of 154 subjects in each group will provide approximately 80% power to reject the hypothesis of the inferiority of PerClot to the composite control by a 10% margin, using a one-sided 97.5% confidence interval (see Appendix A). As the primary endpoint data is collected intraoperatively, no adjustment is made for attrition; however, the sample size was increased to account for the possibility of up to 5% loss within either group due to technical failures (i.e., contraindications, misdiagnosis, or intraoperative death prior to treatment, etc.), and subjects not treated according to randomization assignment, resulting in a sample size of 162 per arm to ensure >80% power. Thus, a total of 324 subjects is the planned sample size to enroll, assuming an efficacy rate of 90%.

A non-inferiority margin of 10% is consistent with the margins used in other controlled clinical trials involving hemostatic agents.^{2, 3} A non-inferiority margin $\delta = 0.10$ was chosen for this study because excluding a 10% difference between the treatments would be supportive of non-inferior performance of PerClot compared to the control.

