4.2.2 Secondary Efficacy

The secondary efficacy objective will be evaluated at 5 minutes in a manner similar to the primary efficacy analysis. The secondary hypothesis for this clinical investigation is that the proportion of subjects achieving hemostasis of the treated bleeding site at 5 minutes in the PerClot group is non-inferior to the proportion of subjects achieving hemostasis of the treated bleeding site at each evaluation time point in the control group.

$$H_0: P_{t,PerClot} < P_{t,Control} - \delta$$
$$H_a: P_{t,PerClot} \geq P_{t,Control} - \delta$$

where $P_{PerClot}$ is the proportion of PerClot subjects achieving hemostasis of the treated bleeding site at time point t , $P_{t,Control}$ is the proportion of control subjects achieving hemostasis of the treated bleeding site at time point t , and δ is the non-inferiority margin, with $\delta = 0.10$.

In other words, the null hypotheses are that the proportion of PerClot subjects achieving hemostasis of the treated bleeding site at each evaluation time point will be inferior to the proportion of control subjects achieving hemostasis of the treated bleeding site at each evaluation time point. The alternative hypotheses are that the proportion of PerClot subjects achieving hemostasis of the treated bleeding site at each evaluation time point will be equal to or greater than, or not inferior to, the proportion of control subjects achieving hemostasis of the treated bleeding site at each evaluation time point. Each null hypothesis will be rejected in favor of the corresponding alternative hypothesis if the upper bound of the 97.5% one-sided confidence interval for the difference in treatment proportions ($P_{t,Control} - P_{t,PerClot}$) is less than 0.10.

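### The 5-minute non-inferiority test is not conditioned on the 7-minute primary, so a formal 5-minute conclusion can follow a failed primary; trial success itself is unaffected

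*SAP*

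**What the plan says.** Protocol 6.6.3 and SAP 4.2.2 set up a formal null and alternative for hemostasis at 5 minutes, with the same 0.10 margin as the primary. SAP 4.2.2 rejects on the upper limit of a one-sided 97.5% interval: "Each null hypothesis will be rejected in favor of the corresponding alternative hypothesis" when that limit is below 0.10. SAP 4.4.3 repeats the rule using the upper end of a 95% interval, which is the same level, and states the consequence: "the null hypothesis will be rejected and treatment will be considered non-inferior to control". SAP 4.4.2 uses the same words for the primary.

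The primary is sized in SAP 4.2.1.1 with "One-sided alpha = 0.025" and "Minimum 80% power". Protocol 6.6.7 and SAP 4.2.3 define trial success as rejection of the 7-minute null in the As Treated population. They do not mention the 5-minute test.

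Where the authors wanted an analysis to be descriptive, they said so: for safety (SAP 4.4.4), for the gender, race and severity subgroups (SAP 4.5), and for the 5-minute results by therapeutic area (Protocol 6.6.3). None of these statements covers the overall 5-minute comparison. Neither document contains a multiplicity rule linking the two time points.

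**The concern.** Two non-inferiority hypotheses, each tested at one-sided 0.025 with nothing linking them, do not hold the chance of any false non-inferiority conclusion at 0.025. What is at stake is the standing of the secondary result. Under the plan as written, a report could state that the 7-minute primary failed and also that PerClot was shown non-inferior at 5 minutes under a pre-specified rule. A reader of that report would have no basis in the SAP for treating the second statement as anything less than confirmatory.

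**Working it through.** **1. The plan's own figure.** Inputs from SAP 4.2.1.1 and Appendix A: 90% in each arm, margin 0.10, one-sided 0.025, 154 per arm, Farrington-Manning score test. The restricted null rates are 0.8313 and 0.9313.

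- Null SD term: √(0.8313×0.1687 + 0.9313×0.0687) = 0.4519
- Alternative SD term: √(2×0.90×0.10) = 0.4243
- Power = Φ[(0.10×√154 − 1.96×0.4519)/0.4243] = 0.79885

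This matches Appendix A, so the primary is sized as described.

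**2. Error across the two tests as written.** With both nulls true at the margin and correlation ρ between the two test statistics:

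- P(at least one false conclusion) = 0.05 − P(both reject)
- P(false 5-minute conclusion only) = 0.025 − P(both reject)

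P(both reject) is the bivariate normal tail beyond 1.96 on both axes.

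| ρ | At least one | 5-minute only |
|---|---|---|
| 0 | 4.94% | 2.44% |
| 0.5 | 4.54% | 2.04% |
| 0.7 | 4.17% | 1.67% |
| 0.8 | 3.90% | 1.40% |
| 0.9 | 3.52% | 1.02% |

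**3. A plausible ρ.** The documents give no 5-minute rates, so these are assumptions: control 70% to 85% at 5 minutes and 90% at 7; PerClot 10 points lower at each time, hence 80% at 7; every 5-minute success still a success at 7. Within an arm, the covariance of the two outcomes is then p5(1 − p7). Summing over arms of equal size:

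ρ = [p5C(1 − p7C) + p5T(1 − p7T)] / √{[p5C(1 − p5C) + p5T(1 − p5T)] × [p7C(1 − p7C) + p7T(1 − p7T)]}

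The 7-minute variance sum is 0.09 + 0.16 = 0.25.

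- Control 70% at 5 minutes, PerClot 60%: ρ = (0.07 + 0.12)/√(0.45×0.25) = 0.19/0.3354 = 0.57. At least one false conclusion 4.4%; 5-minute only 1.9%.
- Control 85%, PerClot 75%: ρ = (0.085 + 0.15)/√(0.315×0.25) = 0.235/0.2806 = 0.84. At least one 3.8%; 5-minute only 1.3%.

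**4. If some early successes re-bleed.** A binomial simulation (400,000 runs, 154 per arm, score test) let 2% of 5-minute successes be lost by 7 minutes, with control at 80% and 85% at 5 minutes. It gave ρ of 0.62 and 0.72, at least one false conclusion in 4.3% and 4.1% of runs, and a 5-minute conclusion alone in 1.9% and 1.6%. In the same runs the primary test rejected in 2.4% to 2.5%, so its own level holds.

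**5. With a gate.** If the 5-minute test is run only after the 7-minute null is rejected, a 5-minute conclusion after a failed primary has probability 0. The error across the two tests is at most 0.025. The primary calculation in step 1 is unchanged.

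**The case against.** The strongest reply is that the decision that matters is already protected. Trial success rests on the 7-minute null alone, with one primary and one secondary endpoint. The stated objectives also separate the two: the primary is to demonstrate non-inferiority, the secondary only to compare. Neither document states a labeling claim for the 5-minute result. All of this stands, and it limits the point to the status of a secondary conclusion. It does not dispose of it, because the secondary hypothesis is written as formal non-inferiority and carries its own rejection rule.

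Four stronger readings are tempting and are not supported:

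- That the SAP says the 5-minute rule applies whatever the primary shows. It says nothing about order; the freedom comes from that silence.
- That the 5-minute test could rescue the trial or inflate the primary's error rate. Protocol 6.6.7 and SAP 4.2.3 rule this out.
- That there are more than two tests, because SAP 4.2.2 sets PerClot at 5 minutes against the proportion "at each evaluation time point in the control group". The displayed hypotheses carry the same time index in both arms, and SAP 4.4.3 analyzes 5 minutes only. The protocol's revision history records removal of a 3-minute assessment, so the plural looks like leftover wording.
- That mixed results under a true 7-minute deficit measure false claims. If PerClot were at 80% against 90% at 7 minutes but equal to control at 5 (75% to 80% in both arms), a failed primary together with a 5-minute non-inferiority conclusion would occur in about 50% to 57% of trials. That 5-minute conclusion would be true, so it is not a Type I error.

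**Conclusion.** The point holds as a gap in how the secondary conclusion is controlled. Following the plan literally permits a formal 5-minute non-inferiority conclusion after the 7-minute primary has failed.

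Its size is moderate: under the step 3 assumptions, the excess over the nominal 2.5% is about 1.3 to 1.9 percentage points, which is the chance of a false 5-minute conclusion standing alone. Those assumptions include PerClot exactly at the margin at both times and early success that persists. SAP 4.4.2 itself allows for re-bleeding between 5 and 7 minutes; the modest re-bleeding tried in step 4 leaves the result in the same range. Even with independent tests, the chance of at least one false conclusion would be 4.94%.

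This is worth correcting before the arms are compared. It casts no doubt on the primary test or on the definition of trial success.

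**What to change.** Add to SAP 4.2.2 and 4.4.3 and to Protocol 6.6.3: *The 5-minute hypothesis is tested at one-sided 0.025 only if the 7-minute null is rejected in the As Treated population; otherwise the 5-minute results are descriptive.*

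As an editorial clean-up only, restate the secondary hypothesis in both documents as PerClot at 5 minutes against control at 5 minutes, in the singular.

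The only cost is that no formal 5-minute conclusion is available when the primary fails. If both arms truly have equal rates (assumed 80% to 85% at 5 minutes, 90% at 7), that happens in about 5% to 6% of trials: the simulated chance that 5 minutes succeeds while 7 minutes fails is 0.052 to 0.057. The planned 154 per arm before loss, and the power of about 80% at that size, stay as they are.

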4.4.4 Safety Analyses

Safety data will be summarized by incidence of each adverse event type along with 95% exact confidence intervals. Adverse event rates will be reported as the proportion of subjects who experience an event and the total number of each event type occurring.

Adverse events will be summarized by relatedness, seriousness, and severity. The comparison of safety between treatment arms will be based on Fisher's exact tests for the proportion of subjects with serious device-related adverse events, unanticipated adverse device effects, and frequent adverse events ($\geq 5\%$ overall incidence) in the two treatment groups.

The other following safety endpoints will also be summarized using descriptive statistics:

- Total operative time;
- Hemostasis at 5 to 7 minutes;
- Hemostasis maintenance;
- Total intraoperative estimated blood loss;
- Alternative means required to achieve hemostasis (where applicable);
- Units of blood transfused intraoperatively and postoperatively (where applicable);
- Incidence of reoperation;
- Total hospitalization time;
- Incidence of procedure complications;
- Incidence of adverse events through final follow-up, including, but not limited to:
 - Adhesions or fibrosis;
 - Anaphylaxis;
 - Blockage of the bladder or ureteral lumen;
 - Blockage of the bypass system;
 - Cancer recurrence and/or progression;
 - Compromised attachment of prosthetic devices to bone or tissue;
 - Death;
 - Embolism;
 - Failure of deep or superficial wound healing;
 - Failure to obtain hemostasis;
 - Fever;
 - Hemorrhage;
 - Infection;
 - Peri-operative hyperglycemia;
 - Exacerbation of surgical procedure-associated adverse events;
 - Swelling and compression of pressure-sensitive tissues and structures;
 - Thromboembolism;
 - Thrombosis; and
 - Toxicity.

Safety analyses are descriptive in nature. There are no formal hypothesis tests associated with these outcomes. All safety analyses will be performed on the ITT population.

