6.6.4 Safety Analysis

Safety data will be summarized by incidence of each adverse event type along with 95% exact confidence intervals. Adverse event rates will be reported as the proportion of subjects who experience an event and the total number of each event type occurring. Adverse events will be summarized by relatedness, seriousness, and severity. The comparison of the safety between treatment arms will be based on Fisher’s exact tests for the proportion of subjects with serious device-related adverse events, unanticipated adverse device effects, and frequent adverse events ($\geq 5\%$ overall incidence) in the two treatment groups.

Additionally, supportive descriptive analyses will be performed on adverse event data within each therapeutic area: open elective cardiac, general, or urological surgical procedures.

The other following safety endpoints will also be summarized using descriptive statistics:

- Total operative time;
- Hemostasis at 5 and 7 minutes;
- Hemostasis maintenance;
- Total intraoperative estimated blood loss;
- Alternative means required to achieve hemostasis (where applicable);
- Units of blood transfused intraoperatively and postoperatively (where applicable);
- Incidence of reoperation;
- Total hospitalization time;
- Incidence of procedure complications;
- Incidence of adverse events through final follow-up, including, but not limited to:
 - Adhesions or fibrosis;
 - Anaphylaxis;
 - Blockage of the bladder or ureteral lumen;

- Blockage of the bypass system;
- Cancer recurrence and/or progression;
- Compromised attachment of prosthetic devices to bone or tissue;
- Death;
- Embolism;
- Failure of deep or superficial wound healing;
- Failure to obtain hemostasis;
- Fever;
- Hemorrhage;
- Infection;
- Peri-operative hyperglycemia;
- Exacerbation of surgical procedure-associated adverse events;
- Swelling and compression of pressure-sensitive tissues and structures;
- Thromboembolism;
- Thrombosis; and
- Toxicity.

6.6.5 *Sample Size Justification*

The sample size was calculated based on the following assumptions:

- One-sided $\alpha = 0.025$;
- Minimum 80% power;
- Non-inferiority margin $\delta = 0.10$;
- Expected 7 minute hemostatic success rate in the PerClot group is 90%;
- Expected 7 minute hemostatic success rate in the control group is 90%; and
- Randomization allocation of 1:1.

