4.5 Subgroup Analysis

Analyses will be conducted to determine the consistency of study results across the following subgroups: gender, race, and bleeding severity score. These analyses will be descriptive in nature, and as such there are no formal hypothesis tests. There are no labeling claims being sought out for these subgroups analyses.

Subgroup analyses will be performed on the primary efficacy measure (proportion achieving hemostasis at 7 minutes), secondary efficacy measure (proportion achieving hemostasis at 5 minutes), and safety measures (proportion with device related events and serious adverse events). For efficacy measures, analyses will be performed on the AT population. Safety subgroup analyses will be based on the ITT population.

For each endpoint measure the proportion of subjects will be reported by subgroup. The difference in proportions and its associated 95% confidence interval will be reported by subgroup. To test for a differential treatment effect across subgroups a logistic regression model will be fit, testing for the interaction of treatment group by subgroup. In the case that poolability across a subgroup is questionable, as indicated by statistical significance of the interaction effect at $\alpha \leq 0.05$, the estimated treatment difference and 95% confidence interval from the subgroup adjusted logistic regression model will be reported.

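### The overall between-arm safety comparison is based on Fisher p-values with no pre-specified interval for the difference, although the SAP gives such an interval for efficacy and for safety within subgroups

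*SAP*

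**What the plan says.** SAP 4.4.4: "The comparison of safety between treatment arms will be based on Fisher's exact tests". The tests apply to the proportions of subjects with serious device-related adverse events, UADEs, and adverse events with at least 5% overall incidence. Protocol 6.6.4 has the same plan: "The comparison of the safety between treatment arms will be based on" Fisher's exact tests for the same three groups.

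The only intervals in SAP 4.4.4 attach to incidences, not to a contrast: "Safety data will be summarized by incidence of each adverse event type along with 95% exact confidence intervals". The section closes with "Safety analyses are descriptive in nature. There are no formal hypothesis tests associated with these outcomes", a statement that Protocol 6.6.4 does not contain. On the analysis set it says "All safety analyses will be performed on the ITT population".

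Elsewhere the SAP does specify an interval for the contrast. Sections 4.4.2 and 4.4.3 report the difference in hemostasis proportions at 7 and 5 minutes with its 95% confidence interval. Section 4.5 covers device-related events and serious adverse events within gender, race and bleeding-severity subgroups: "The difference in proportions and its associated 95% confidence interval will be reported by subgroup".

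**The concern.** The stated overall objective covers the safety as well as the efficacy of PerClot against an active control. For safety, the useful question is how large an excess of harm the data still allow. A Fisher p-value does not answer it. When events are rare, a non-significant result is likely whether or not a relevant excess exists.

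Two features of the plan make the gap visible. First, the SAP pre-specifies an interval for the safety difference in small subgroups but not for the whole trial, where it would be most informative. Second, SAP 4.4.4 bases the comparison on tests and then disclaims formal tests, so the status of the p-values is unclear. At stake is the interpretation of the safety results. The trial success rule (SAP 4.2.3) concerns efficacy only and is not affected.

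**Working it through.** **Inputs from the documents.** 162 per arm planned (SAP 4.2.1.1); maximum total 536, so 536 / 2 = 268 per arm (SAP 4.2.1.2); 1:1 allocation; safety analysed in all randomized subjects. **Assumptions.** Fisher tests two-sided at 0.05, because no level or sidedness is stated for them; all subjects evaluable; event rates chosen for illustration, because the documents give none.

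**1. The plan's own figure.** The documents give no power for safety. The efficacy power in SAP Appendix A can be reproduced. With 90% v 90%, margin 0.10 and 154 per arm, the Farrington-Manning restricted estimates are 0.8313 and 0.9313.
- SE under the null = sqrt[(0.8313 × 0.1687 + 0.9313 × 0.0687) / 154] = 0.03641
- SE under the alternative = sqrt(2 × 0.09 / 154) = 0.03419
- Power = Φ[(0.10 − 1.96 × 0.03641) / 0.03419] = Φ(0.8375) = 0.7988, against the stated 0.79885

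The loss allowance gives 154 × 1.05 = 161.7, rounded up to 162.

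**2. Fisher power for a doubling.** Exact power is the sum of Bin(x; n, p1) × Bin(y; n, p0) over all pairs (x, y) with two-sided Fisher p ≤ 0.05.

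| Control v PerClot | 162 per arm | 268 per arm |
|---|---|---|
| 1% v 2% | 2.7% | 7.6% |
| 2% v 4% | 9.8% | 19.5% |
| 3% v 6% | 16.9% | 32.0% |
| 5% v 10% | 32.1% | 53.8% |
| 10% v 20% | 66.9% | 88.5% |

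Power for a doubling passes 50% at a control rate of about 7.4% with 162 per arm, and about 4.6% with 268.

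**3. What an interval adds, 162 per arm.** Take 16 v 8 events. The difference is 16/162 − 8/162 = 9.9% − 4.9% = 4.9 points. Fisher p = 0.136; the 95% score interval is -0.8 to +11.0 points. The p-value alone hides that an 11-point excess is still compatible with the data.

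**4. Very rare events, 162 per arm.** For 5 v 0, p = 2 × (162·161·160·159·158) / (324·323·322·321·320) = 0.061. For 6 v 0, the further factor 157/319 gives p = 0.030. So six events against none are needed to reach 0.05. For 5 v 0 the 95% score interval is +0.7 to +7.0 points and excludes zero; for 4 v 0, p = 0.12 and the interval is +0.1 to +6.2. The two statistics can disagree, so a plan that reports both needs a reading rule.

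**The case against.** The strongest counter-case has five parts.

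- **The power loss depends on the event rate.** A reader might infer that a doubling of harm would usually be missed. The documents do not support that: they give no event rates, and a 10% v 20% doubling is detected 67% of the time at 162 per arm. This limit stands.
- **The SAP does contain safety intervals.** A reader might infer that Fisher tests are the only safety contrast in the SAP. Section 4.5 shows otherwise. But its intervals are by subgroup only, so it confirms the overall gap rather than closing it.
- **The interval can be computed later.** A reader might infer that the trial could not say what excess it has excluded. That is too strong: the reported proportions allow anyone to calculate the interval. What is missing is pre-specification.
- **Nothing says non-significance will be read as comparable safety.** This is true, there is no safety non-inferiority claim, and SAP 4.4.4 already calls the analyses descriptive. One can reconcile its sentences by treating the p-values as descriptive, but the section does not say so and the protocol has no such sentence.
- **Individual UADEs would not be dismissed on a p-value.** They are evaluated singly and reported within 10 working days (Protocol 9.3.1), and the data safety monitoring board reviews accumulating safety data (Protocol 9.4). This limits the practical risk for UADEs, but not for the summary comparison of the other event groups.

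**Conclusion.** The point holds as a gap in pre-specification. The overall safety comparison is test-based and has no planned interval for the difference, while the SAP supplies one for efficacy and for safety subgroups. The wording in SAP 4.4.4 leaves the status of the tests unclear.

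The practical effect is largest for rare harms. At 162 per arm, a doubling from a control rate of 3% or less would be missed in more than 80% of trials (power 16.9% or below). It shrinks as events become common. These figures rest on a two-sided 0.05 level and on assumed rates. They do not show that the safety data would be uninterpretable, or that the sponsor intends to treat a non-significant result as proof of equal safety. This is a cheap improvement and does not threaten the trial's conclusion on efficacy.

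**What to change.** In SAP 4.4.4 and Protocol 6.6.4, for the same three event groups:

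1. Base the between-arm comparison on the overall risk difference (PerClot minus control) with its 95% confidence interval by a named method, such as the score interval.
2. Keep the Fisher p-values, labelled as descriptive only. Put the same statement on the status of safety tests in both documents.
3. State that the interval governs interpretation where it and the p-value disagree, as with 5 v 0 events.
4. State that a non-significant p-value will not be reported as evidence of comparable safety.

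The cost is a wording change in two sections and one extra column in existing tables, with no added subjects or data collection. The downsides are that the intervals will be wide and will sometimes disagree with the Fisher p-value for rare events, which is why item 3 is needed.

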4.2 Potential Risks

There are possible risks, complications, and discomforts associated with surgery in general. The more common and serious possible risks and/or complications of surgeries include, but are not limited to, the following:^{10,11}

- Abscess formation;
- Adhesion formation;
- Allergic reactions to any drugs given during surgery;
- Anesthesia complications;
- Arrhythmia;
- Atelectasis;
- Bleeding;
- Death;
- Deep vein thrombosis;
- Fluid collection;
- Hematoma;
- Hemothorax;
- Hypoxemia;
- Infection;
- Myocardial infarction;
- Pain;
- Paralysis;
- Pneumothorax;
- Pulmonary embolism;
- Reoccurrence of chest pain;
- Stroke; or
- Tissue necrosis.

Furthermore, there are possible risks, complications, and discomforts specifically associated with the three therapeutic areas (cardiac, general, and urological). The more common and serious risks and/or complications associated with these three therapeutic surgical areas include, but are not limited to, the following:

Cardiac^{12, 13, 14, 15}

- Brain damage;
- Graft failure;
- Infection of the inner tissue lining of the heart (endocarditis);
- Infection of the mediastinum, the cavity between the lungs (mediastinitis);
- Inflammation (pericarditis);
- Irregular heart rhythm; or
- Post-pericardiotomy syndrome.

General^{16, 17}

- Ascites;
- Biliary leakage;
- Hernia formation;
- Necrotizing pancreatitis;
- Pleural effusion; or
- Pneumonia.

Urological^{18, 19, 20}

- Epididymitis;
- Fistula;
- Sexual dysfunction;
- Unanticipated loss of renal function;
- Ureteral injury;
- Urinary incontinence; or
- Urinary leak.

Subjects that are randomized to the control group are exposed to increased risks associated with the use of Arista™ AH (Medafor, Inc.; Minneapolis, MN; hereinafter referred to as Arista). Possible adverse events that could be associated with the use of Arista may include, but are not limited to, the following:²¹

- Act as foci for calculus formation when used in renal pelvis or ureters;
- Compression of the brain and spinal cord resulting from the accumulation of sterile fluid;
- Compression necrosis of surrounding tissues due to swelling;
- Compromised attachment of prosthetic devices to bone or tissue;
- Death;
- Effect on glucose load;
- Embolization; and
- Paralysis and nerve damage when used in or in proximity to foramina in bone, areas of bony confine, the spinal cord, and/or the optic nerve and chiasm.

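### No between-arm difference or test is planned for any-cause SAEs overall, or for named risks, death or reoperation that are under 5% and not graded serious and device-related or a UADE

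*SAP*

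**What the plan says.** SAP 4.4.4 has three layers.

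- **Every event type:** "Safety data will be summarized by incidence of each adverse event type along with 95% exact confidence intervals". Subject proportions and event counts are reported, with summaries by relatedness, seriousness and severity. The section does not say outright that these incidences are tabulated by arm.
- **Comparison between arms:** Fisher's "exact tests for the proportion of subjects with serious device-related adverse events, unanticipated adverse device effects, and frequent adverse events". The third category is limited to event types reaching 5% "overall incidence) in the two treatment groups".
- **Everything else:** "The other following safety endpoints will also be summarized using descriptive statistics". The list that follows includes reoperation and 19 named adverse events, among them death, embolism, thromboembolism, thrombosis, anaphylaxis and infection.

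The section closes with "Safety analyses are descriptive in nature. There are no formal hypothesis tests associated with these outcomes", and adds "All safety analyses will be performed on the ITT population". Protocol 6.6.4 carries the same three Fisher categories and the same list, without the closing statement about formal tests.

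Three other places matter. Protocol 9.2 has the Investigator grade the relation to the device. SAP section 3 blinds subjects only. SAP 4.5 reports a difference in proportions with 95% CI for "safety measures (proportion with device related events and serious adverse events"), but only within gender, race and bleeding severity subgroups.

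**The concern.** The stated overall objective is to collect data on safety as well as efficacy against a marketed comparator. Efficacy gets a difference with a 95% CI. For safety, whether an event is compared at all depends on one of three gates.

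Two of the gates are weak for the risks of most interest. The first needs a judgement that the device was involved, made by an investigator from whom nothing in the plan conceals the arm. The third needs a pooled frequency of 5%. An event that can follow from surgery itself may be graded unrelated; protocol 4.2 lists deep vein thrombosis and pulmonary embolism among general surgical risks. If it is also below 5% and not a UADE, no comparison category takes it in. The sponsor's risk analysis (protocol Appendix C) rates intravascular administration, with embolism and death among its effects, at severity grade 5 both before and after mitigation, so these are not minor events.

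The plan is also uneven. SAP 4.5 asks for the difference in serious adverse events inside subgroups, but no section asks for it in the whole trial. If an imbalance appears, someone will have to decide after seeing the data which differences to estimate.

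**Working it through.** **Inputs.** SAP 4.2.1.1: 154 per arm before loss, up to 5% loss, 162 per arm, 324 in total, 1:1 allocation. SAP 4.2.1.2: maximum 536. SAP 4.4.4: threshold of 5% overall incidence, ITT population.

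**Denominator.** The score-test formula gives power 0.7988 at 154 per arm, against 0.79885 in SAP Appendix A. Then 154 × 1.05 = 161.7, rounded up to 162, and 2 × 162 = 324. The plan's figures reproduce.

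**Where the 5% rule bites.** 0.05 × 324 = 16.2, so 17 subjects are needed; 16/324 = 4.94% falls short. At the maximum, 0.05 × 536 = 26.8, so 27 are needed; 26/536 = 4.85% falls short.

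**Illustration.** Take 16 affected subjects split 14 against 2. The split is hypothetical; the documents give no expected rates for these events.

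- Rates: 14/162 = 8.64% and 2/162 = 1.23%; difference 12/162 = 7.4 points.
- Wilson 95% limits: 5.22% to 13.98%, and 0.34% to 4.39%.
- Newcombe lower limit: 7.41 − √[(8.64 − 5.22)² + (4.39 − 1.23)²] = 2.8.
- Newcombe upper limit: 7.41 + √[(13.98 − 8.64)² + (1.23 − 0.34)²] = 12.8.
- Fisher two-sided, equal arms: p = 2 × P(X ≥ 14), with X hypergeometric given 16 events in 324. p = 0.0034.

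**Other splits, two-sided Fisher p.**

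| Split | Per arm | Overall | p | Passes the 5% rule? |
|---|---|---|---|---|
| 15 vs 2 | 162 | 5.25% | 0.0018 | yes |
| 14 vs 2 | 162 | 4.94% | 0.0034 | no |
| 13 vs 3 | 162 | 4.94% | 0.018 | no |
| 12 vs 4 | 162 | 4.94% | 0.070 | no |
| 11 vs 5 | 162 | 4.94% | 0.20 | no |
| 8 vs 1 | 162 | 2.78% | 0.036 | no |
| 6 vs 0 | 162 | 1.85% | 0.030 | no |
| 5 vs 0 | 162 | 1.54% | 0.061 | no |
| 20 vs 6 | 268 | 4.85% | 0.008 | no |

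**What the plan would still show.** The exact 95% intervals per arm for 14 and 2 of 162 are 4.8% to 14.1% and 0.1% to 4.4%. They do not overlap, so incidences tabulated by arm would make the imbalance visible.

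**How often the filter would act.** If the true rates were 14/162 and 2/162, the chance that the pooled count is 16 or fewer is 0.57, taking the two arms as independent binomials.

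**The case against.** **The imbalance is not hidden.** Each event type gets an incidence with an exact interval, and the DSMB reviews accumulating safety data (protocol 9.4). This stands. A reader might infer that such an event gets no comparison of any kind, but the documents do not support that. What is missing is a between-arm difference with CI, or a test.

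**Attribution does not govern everything.** The 5% category needs no attribution. Events graded serious and device-related enter the first test in aggregate, and a listed risk can still be a UADE through its severity or degree of incidence (protocol 9.1). This stands too, so the gap is conditional on grading and frequency.

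**The illustration sits one subject below the cutoff.** Partly fair: 12 vs 4 and 5 vs 0 are unremarkable. But 6 vs 0 and 8 vs 1 lie well below the cutoff, and enlarging the trial does not remove the problem.

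**The UADE category.** A reader might infer that UADEs are biased between arms because protocol 4.2 gives Arista its own list ("Possible adverse events that could be associated with the use of Arista may include, but are not limited to"). That does not follow. The two lists share death and compromised prosthetic attachment, and embolization corresponds to embolism. Infection, bleeding and deep vein thrombosis are listed as general surgical risks for all subjects, and protocol 6.1.3 names all 19 events without distinguishing arms. Nothing says anticipation is judged from an arm-specific list.

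**Fisher tests against no formal tests.** This is mostly wording. The closing sentence follows the descriptive list, and a p-value with no alpha can be descriptive. A clarifying phrase settles it.

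**Conclusion.** The concern holds in a limited form. SAP 4.4.4 and protocol 6.6.4 specify a between-arm comparison for three categories only. Any-cause SAEs overall have no planned difference, interval or test, and neither do named risks, death or reoperation outside those categories. At 324 subjects this can leave uncompared a difference as large as 7.4 points (95% CI 2.8 to 12.8). That figure assumes full enrolment at 162 per arm, a hypothetical 14 to 2 split, and events neither graded serious and device-related nor classed as UADEs. That the grading investigator knows the arm is an inference from subject-only blinding. The efficacy conclusion is unaffected. This is a gap in a safety analysis the SAP itself calls descriptive, worth closing because it is cheap and the trial sets out to compare safety.

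**What to change.** Keep the existing Fisher comparisons. Replacing them would lose the comparison of frequent events that are not on the named list. In both SAP 4.4.4 and protocol 6.6.4, add:

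1. The by-arm risk difference with 95% CI, regardless of attribution or frequency, for any SAE, death, reoperation and each adverse event named in SAP 4.4.4.
2. A statement that these intervals and the Fisher p-values are descriptive, with no alpha attached.

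Both documents must change together, or they will disagree. The adverse event and reoperation forms already collect the data, so the cost is wording and some table rows. The downside is more descriptive intervals, some of which will look notable by chance.
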